### Specific Aims

Specific Aim 1: To enhance and evaluate the validity of a self-report assessment of tobacco withdrawal, the revised Wisconsin Smoking Withdrawal Scales-2 (long: WSWS2-L; brief: WSWS2-B), in terms of their sensitivity to smoking abstinence in initially unmedicated individuals making a quit smoking attempt.

Specific Aim 2: To compare the validity of the WSWS2-L and the WSWS2-B with alternative withdrawal scales on the bases of psychometric criteria.

Specific Aim 3: To determine factors that most accurately predict withdrawal severity (peak, average, variability, and duration), including contextual factors, personality factors, lifestyle factors, pharmacologic factors, precessation symptomatology, reward sensitivity/response, and affective processing dimensions.

### Significance

The Wisconsin Smoking Withdrawal Scale (WSWS) was developed over two decades ago to provide researchers and clinicians with a psychometrically sound, validated self-report assessment of nicotine withdrawal (Welsch et al., 1999). This 28-item scale includes a total symptom scale and 7 subscales addressing components of the tobacco withdrawal syndrome (e.g., anxiety, anger, sadness, craving, concentration difficulties, hunger, and sleep problems). The original scale has reasonable psychometric properties, is sensitive to smoking abstinence, related to tobacco dependence measures, and has moderate predictive validity regarding smoking cessation outcomes. The WSWS has been a valuable assessment instrument that has been used by numerous researchers worldwide for investigating the nature and correlates of tobacco withdrawal. However, the field's understanding of tobacco withdrawal has advanced in recent years and the population of smokers has changed substantially (e.g., reduced smoking heaviness; Jamal et al., 2018). Thus, there is a clear need to update and improve the assessment of withdrawal.

It is of considerable scientific and clinical importance to assess tobacco withdrawal accurately since withdrawal severity is highly determinant of smoking cessation success. In addition, smoking cessation pharmacotherapy produces its effects on smoking abstinence by suppressing such symptoms (Bolt et al., 2012). The current study aims to validate, and possibly enhance, a revised WSWS for use in research and clinical settings. We have recently

developed a psychometrically robust, revised version of the WSWS based on several recent smoking cessation trials conducted by UW-CTRI (WSWS2, Smith et al., in press). However, most previous research, including our own, has occurred within the context of the pharmacological treatment of smoking. In order to ensure that a measure of tobacco withdrawal is sensitive to severe withdrawal, it is essential to examine unmedicated smokers. Unmedicated smokers display withdrawal symptoms that vary greatly in severity, which will allow us to determine which WSWS2 items are sensitive to both mild and severe withdrawal symptomatology. Assessment of unmedicated withdrawal is rarely done and therefore this research will yield unusual and valuable data on withdrawal amongst today's smokers. It is also important to assess withdrawal amongst smokers who are using smoking medications since treatment guidelines (Fiore et al., 2008) recommend that virtually all smokers in formal treatment programs use such medication. Therefore, data gathered from smokers when they begin using medication will be highly relevant to the greater population of treated smokers.

The current study aims to validate a revised WSWS measure (WSWS2-L) in a new sample of unmedicated smokers who abstain from smoking for 1 week prior to receiving pharmacological smoking cessation treatment. Furthermore, the research will evaluate constructs that have emerged primarily in recent years for possible inclusion in the new WSWS (e.g., restlessness, anhedonia, pain). Depending on the results of such evaluation, items representing these constructs may be included in a future version of the WSWS instrument. Another reason for conducting more research on the WSWS is that the previous measure was quite lengthy, which reduced its routine use in both clinical and research contexts due to concerns over assessment burden. Therefore, the proposed research will validate a psychometrically valid short form of this instrument (the Brief WSWS2: the WSWS2-B) in addition to a longer form suited for in-depth analysis of withdrawal (WSWS2-L). Developing a short form is especially vital given the increasing use of mobile technology for assessment. Such technologies require the use of very brief but valid assessment instruments. As such, this study aims to validate both a full yet efficient comprehensive WSWS2-L as well as a brief and focused WSWS2-B for use across diverse clinical and research settings.

## **Study Overview**

We propose recruiting up to 500 daily cigarette smokers who report a desire to quit smoking in order to enroll up to 250 participants. This is a treatment-delay, one-group clinical trial that is intended to enhance the assessment of tobacco withdrawal amongst participants who try to quit smoking with delayed use of cessation medication. In addition, it is intended to identify important determinants of withdrawal severity. Participants will not receive any pharmacotherapy during the first 1 week of their quit attempt. They will initiate pharmacotherapy 1 week past the target quit day (TQD) and continue treatment through 9 weeks past the TQD. This will allow for the examination of withdrawal symptoms for 1 week post-TQD in participants who are not using pharmacotherapy. Participants will receive 8 weeks of combination nicotine replacement therapy (C-NRT: nicotine patch + nicotine mini-lozenge) starting 1 week past the TQD. Participants will receive 4 counseling sessions that conform to the US PHS Clinical Practice Guideline recommendations (1 prequit, 3 postquit). Participants will complete 4 weeks of ecological momentary assessment (EMA) including a 2-week baseline (starting TQD-14) and 2-week post-TQD (1-week un-medicated, 1-week using C-NRT). Participants will be recruited via media (newspaper and television advertisements, and Facebook advertisements) to attend an Orientation Visit where the study will be explained and they will provide written informed consent. Once consented, the study will include three phases (described below): Orientation, Precessation and Cessation. Over the 2-week Precessation and the first 2 weeks of the

Cessation phase, participants will complete intensive daily mobile self-report assessment (mobile assessment) of withdrawal and other relevant variables.

*The Orientation Phase.* This will include an Orientation session for all participants and will entail completion of written informed consent, eligibility screening, a self-report assessment battery, and physical assessments (e.g., breath CO, urine nicotine/cotinine levels, blood pressure). Assessments delivered during these visits will include withdrawal assessment, smoking heaviness, use of all nicotine products, and potential mechanisms of treatment (e.g., expectations of smoking reinforcement, smoking contexts, affect). Eligible participants will be scheduled for a Precessation Call.

*The Precessation Phase.* This will include all participants (n=250) and last 2 weeks, ending at the participant's TQD. Participants will have 3 phone calls during this phase: at around 2 weeks, 1 week, and 1 to 3 days before the TQD. They will continue their normal ad lib smoking and receive no medication during this phase. They will complete 2 weeks of intensive daily mobile self-report assessment (via ecological momentary assessment; EMA) of tobacco withdrawal and related factors prior to the TQD. Counseling will be provided at 1 week before the TQD. This visit will encourage all participants to review their motivation for quitting and ensure that they have a good quit plan for their TQD (e.g., abstaining completely on their TQD). Counseling sessions will be audio recorded for quality assurance. The extensive withdrawal assessment battery will be repeated at the study calls and any EMA problems will be addressed.

*The Cessation Phase.* This will start on the TQD and will last 9 weeks. Participants will attend 2 study visits and 1 study call during the first two weeks of this phase: at 1-2 days post-TQD (call), 7 days post-TQD (visit), and 2 weeks post-TQD (visit). During these calls and visits participants will be given cessation counseling (15-20 min) that stresses complete abstinence from cigarettes and that is consistent with the PHS Smoking Cessation Clinical Practice Guideline (Fiore et al., 2008). Counseling at the 1-week and 2-week visits will also stress adherent medication use and ways to deal with medication side effects. Counseling sessions will be audio recorded for quality assurance. Extensive withdrawal assessment battery will be repeated at the study visit and calls. At the study visits physical assessment will include breath CO, urine nicotine/cotinine levels, and blood pressure. Participants will be given their medication at the study visit 1-week post-TQD and instructed to start using their medication the next day. At these study visits and calls we will assess withdrawal and relevant factors as well as timing of any lapses. Participants will receive 1 additional assessment study phone calls during this phase at 63 days post-TQD (9 weeks). This phone call will assess smoking status, withdrawal, medication adherence, and medication side effects. Participants who report abstinence at this call will be asked to attend an in-person visit for biochemical verification of abstinence (e.g., breath CO). Urine nicotine/cotinine levels will also be measured.

## **Participants**

Two hundred participants (age  $\geq 21$ ; 50% women) who smoke  $\geq 5$  cigarettes per day, have a CO level  $\geq 5$  ppm, and report a desire to quit smoking, will be recruited from Madison and Milwaukee, WI. Participants must be willing to attempt to abstain from smoking for 1 week without the use of pharmacotherapy treatment or other nicotine use (e.g., e-cigarettes). See sections below for details on eligibility criteria, recruiting, and participant compensation strategies to enhance retention.

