### **Power and Sample Size Justification**

Based on the average expected communalities and the variables-to-factors ratio (factor overdetermination) of the proposed analyses, we believe the sample sizes proposed will provide good power the exploratory factor analyses and other covariance structural modeling (R. C. MacCallum et al., 2001; Robert C. MacCallum et al., 1999). A key prediction concerns the relation between a dichotomized scoring of the WSWS-2B and likelihood of abstinence at follow-up. We propose that those with low withdrawal scores will have an abstinence likelihood

of .40 while those with a high score will have an abstinence likelihood of .20. Assuming  $p=.05$  and  $B=.80$ , the  $N$  for a regression of .20 = 95 (Hsieh et al., 1998). Therefore, we believe the design is adequately powered for the expected results, which would be of clinical significance.

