## **Protection of Human Subjects**

### **Risks to the Participants**

***Human Subjects Involvement and Characteristics:*** Up to 400 adult smokers will be consented from the community in order to enroll at least 250 participants. Participants must: have the ability to read and write in English, smoke  $\geq 5$  cigarettes per day, be  $\geq 21$  years old, desire to quit smoking but not be engaged currently in cessation treatment, expired breath carbon monoxide  $\geq 5$  ppm, willing to use nicotine patch and nicotine lozenge, willing and able to attend study visits, have reliable smartphone access, willing to respond to EMA prompts and other study activities, and if female, not be pregnant, trying to get pregnant, or breastfeeding. Exclusion criteria include: use of pipe tobacco, cigars, snuff, chew, e-cigarettes/vaping, or other electronic nicotine delivery product more than twice in the past week, unwilling to try to abstain from all nicotine use (including e-cigarettes) for the duration of the Cessation Phase (other than study-provided NRT), currently taking varenicline or bupropion, diagnosis of and/or treatment for schizophrenia, other psychotic disorder, or bipolar disorder within the last 5 years; suicide attempt or suicidal ideation in the past 12 months; severe hypertension ( $>180/100$  mmHg), on dialysis or being told you have severe kidney disease; hospitalization for a stroke, heart attack, congestive heart failure or uncontrolled diabetes mellitus within the past year; currently participating in a smoking cessation study, or unwilling to use study approved methods of birth control while taking study medication and for 1 month after discontinuing study medication (only for women of child-bearing potential). Study approved methods of birth control include abstinence from sex with men, condoms, diaphragm, birth control pills, injectable contraceptive (e.g., Depo-Provera), contraceptive implant (e.g., Implanon), IUD, have had hysterectomy or tubal ligation, or are more than 2 years post-menopausal.

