## Study Overview

Adults who smoked cigarettes daily and desired to quit smoking enrolled in this study (N=232). This treatment-delay, one-group clinical trial was intended to validate and/or enhance the assessment of tobacco withdrawal amongst participants who try to quit smoking without using

medication early in the course of their quit attempt. Participants attempted to quit smoking and were instructed not to use any smoking cessation pharmacotherapy during the first week of their quit attempt. They initiated pharmacotherapy 1 week past the target quit day (TQD) and continued pharmacotherapy through 9 weeks past the TQD. This will allow for the examination of withdrawal symptoms for 1-week post-TQD in participants who are not using pharmacotherapy. Participants received 8 weeks of combination nicotine replacement therapy (C-NRT: nicotine patch + nicotine mini-lozenge) starting 1 week past the TQD. Participants received 4 counseling sessions (1 pre-TQD, 3 post-TQD) that conform to the US PHS Clinical Practice Guideline recommendations (Fiore et al., 2008). Participants completed 4 weeks of ecological momentary assessment (EMA) including a 2-week baseline (starting TQD -14d) and 2-week post-TQD (1-week un-medicated, 1-week using C-NRT). Enrolled participants completed an Orientation Phase, Pre-cessation Phase, Cessation Phase, and Follow-up Phase (Visit 4 only if self-reported 7d point prevalence abstinence). See Tables 1-3 below for timing of assessment and study activities.

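### Planned enrolment is given as 200, a ceiling of 250, exactly 250 and a floor of 250, so the size behind the power claim is not identified and the 232 enrolled cannot be judged against a target

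*Protocol*

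**What the plan says.** Four statements in the current protocol text give the planned enrolment:

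- Participants: "Two hundred participants" are to be recruited.
- Study Overview, opening paragraph: recruitment is planned "in order to enroll up to 250 participants", which is a maximum.
- Study Overview, Precessation Phase: "This will include all participants (n=250) and last 2 weeks", which is a fixed number.
- Risks to the Participants: people are to be consented "in order to enroll at least 250 participants", which is a minimum.

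The Power and Sample Size Justification does not choose among them. For the factor analyses and covariance structure modelling it says "we believe the sample sizes proposed will provide good power the exploratory factor analyses" and gives no number. For its one quantified contrast (abstinence of .40 with a low WSWS2-B score against .20 with a high score, alpha .05, power .80) it states a required N of 95 and concludes that the design is adequately powered. It does not give sidedness, the split between low and high scores, or an allowance for missing outcomes.

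The SAP's Study Overview describes those who "enrolled in this study (N=232". It gives no planned figure for comparison.

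**The concern.** The planned size cannot be 200 and 250, and 250 cannot be both the most and the least that will be enrolled. Two things depend on which is meant.

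First, the factor-analysis power claim is tied to the planned size and to nothing else. Validating the scale is the main purpose of the trial, and a reader cannot check a claim whose N could be 200 or 250.

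Second, the report will have to say how enrolment compared with plan. The protocol is to be published with the primary outcome paper, so readers will find four answers and no rule for choosing one.

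The stated requirement of 95 might seem to make the choice irrelevant, since every candidate size is about twice that. Whether it does depends on whether 95 is right, so that is checked as well.

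**Working it through.** **Inputs from the protocol's power section:** p₁ = .40, p₂ = .20, alpha .05, power .80, stated N = 95. **Assumed, because not stated:** two-sided test, equal split, and loss of 0% to 40%. **Candidate sizes:** 200 and 250 (protocol), 232 (SAP).

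**1. The plan's own figure.** With pooled null variance, the number per group is

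n = [1.960·√(2·p̄(1−p̄)) + 0.8416·√(p₁(1−p₁) + p₂(1−p₂))]² / (p₁−p₂)²

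with p̄ = .30. Hence n = (1.960 × 0.6481 + 0.8416 × 0.6325)² / 0.04 = 81.2, rounded up to 82 per group, or 164 in total. The stated 95 is not reproduced. Variants tried:

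| Method | N |
|---|---|
| Two proportions, two-sided, equal split | 164 total (82 per group) |
| Same, with continuity correction | 182 total (91 per group) |
| Two proportions, one-sided | 128 total; 148 with continuity correction |
| Logistic regression, binary covariate, two-sided, equal split | 162.4 |
| Same, 30/70 split | 186 to 198 |
| Logistic regression, continuous covariate, log OR = ln 2.667, overall rate .2 to .5, two-sided | 33 to 51 |
| Correlation of .20, two-sided | 194 |

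None gives 95, either as a total or per group.

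**2. Power at each size, equal split, no loss.** Power = Φ[(0.20 − 1.960·s₀)/s₁], where s₀ = √(0.21 × 4/N) and s₁ = √(0.40 × 2/N).

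| N | s₀ | s₁ | Argument of Φ | Power |
|---|---|---|---|---|
| 95 | 0.0940 | 0.0918 | 0.171 | 56.8% |
| 200 | 0.0648 | 0.0632 | 1.154 | 87.6% |
| 232 | 0.0602 | 0.0587 | 1.398 | 91.9% |
| 250 | 0.0580 | 0.0566 | 1.527 | 93.7% |

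**3. Power after loss of outcomes, equal split.**

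| Assumed loss | 200 | 232 | 250 |
|---|---|---|---|
| 10% | 83.9% | 88.9% | 91.1% |
| 20% | 79.4% | 85.0% | 87.6% |
| 30% | 73.8% | 80.0% | 82.9% |
| 40% | 67.0% | 73.6% | 76.7% |

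The loss at which the analysed number falls to 164 is 1 − 164/200 = 18% for 200, 1 − 164/232 = 29% for 232, and 1 − 164/250 = 34% for 250.

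**4. Uneven split.** With no loss, power stays at or above 80% for a low-score share of about 27% to 70% at 200, 21% to 76% at 232 and 19% to 78% at 250. With a 30/70 split, 232 gives 86% to 88% without loss and about 77% to 80% with 20% loss. The range reflects which group is the smaller.

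**5. Enrolment against plan.** 232/200 = 116%. 232 ≤ 250, so the ceiling is respected. 250 − 232 = 18, and 18/250 = 7.2% below the floor.

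**The case against.** The best defence is that nothing turns on the discrepancy. All three sizes exceed the stated 95, and they also exceed the recomputed 164. Enrolment has closed, the enrolled number is known to be 232, and at that size the contrast has about 92% power on complete data and an even split. The results below 80% at 200 need a loss rate the documents do not give, and a size that was not the one enrolled. Most of this stands. What does not stand is the appeal to 95, which does not follow from the protocol's inputs. Nor does the argument reach the factor-analysis claim, which has no N at all.

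A further objection is that the SAP's Predictive Validity section uses the estimated jump, mean and trajectory of withdrawal and does not mention a dichotomised score. Power restated for that contrast would then describe an analysis the SAP does not specify. This is fair, and it is a reason to allow precision for the SAP's own estimates as an alternative.

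Three stronger readings are tempting, and the documents do not support them:

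- *The trial missed its minimum enrolment.* This holds only against Risks to the Participants. The Study Overview makes 250 a maximum and the Participants section plans 200. While the target is ambiguous, a miss cannot be asserted.
- *The trial is underpowered.* The calculations above do not show this for 232.
- *The upstream counts also conflict* (up to 500 in Study Overview, up to 400 in Risks to the Participants). The first counts people recruited and the second people consented. Recruitment and phone screening come before written consent, so the two can differ.

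**Conclusion.** The point holds as an inconsistency in a figure the trial relies on. Planned enrolment is stated in four incompatible ways, the power section does not say which it uses, and the 232 enrolled therefore cannot be classed as on target or short of it.

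The effect on the quantified contrast is modest. Moving from 200 to 250 changes power by about 6 percentage points on complete data (87.6% to 93.7%) and about 8 with 20% loss (79.4% to 87.6%); of these, only 200 with 20% loss falls below the stated .80, and then only just. These figures rest on a two-sided test, an equal split and the loss rates shown, all of which are assumptions.

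The larger numerical fault lies in the same section: 95 gives about 57% power on the section's own inputs, against about 164 needed. Both should be corrected together, since 95 is what makes the choice of planned size look immaterial.

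**What to change.** - State one planned enrolment figure in Study Overview (both places), Participants and Risks to the Participants. Label it as target, maximum or minimum, and cite it in Power and Sample Size Justification as the size behind the factor-analysis claim.
- In that section, replace 95 with the recomputed total (about 164 for a two-sided test and an equal split). State the sidedness, the split of the dichotomised score and the allowance for loss.
- In the SAP and the report, set the 232 enrolled against the planned figure. Give power or precision for 232 and for the number analysable at the follow-up the power section means, and say which follow-up that is.

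The cost is wording and a short recalculation. No further enrolment is proposed. The downside is that the trial may have to report a shortfall of 18 and a slightly less favourable figure.

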## **Inclusion/Exclusion Criteria**

*Self-reported inclusion criteria:*

- Smoke ≥5 cigarettes per day for past year
- ≥21 years old
- Able to read and write English
- Desire to quit smoking
- Not currently engaged in cessation treatment
- Eligible to use combination nicotine replacement therapy
- Willing and able to attend study visits
- Have reliable smartphone access
- Not currently pregnant, trying to get pregnant, or breastfeeding
- Willing to respond to ecological momentary assessment prompts and other study activities

*Other inclusion criteria:*

- Baseline breath carbon monoxide (CO) ≥5 ppm

*Self-reported exclusion criteria:*

- Used pipe tobacco, cigars, snuff, or chew more than twice in the past week
- Used e-cigarette, vaping, or any other electronic nicotine delivery product more than twice in the past week
- Unwilling to try to abstain from all non-medicinal nicotine use (including e-cigarettes) for the duration of the Cessation Phase (other than nicotine replacement therapy provided by the study)
- Currently taking varenicline or bupropion
- Allergy to adhesive tape
- Previous reaction to the nicotine patch or mini-lozenge that prevented them from continuing to use it
- Unwilling to use study approved methods of birth control while taking study medication and for 1 month after discontinuing study medication [only for women of child-bearing potential]
- Hospitalized for a stroke, heart attack, congestive heart failure, ulcers, or diabetes within the last year
- History of seizure within the last year
- Diagnosis of and/or treatment for schizophrenia, other psychotic disorders, or bipolar disorder within the last 5 years
- End-stage renal disease
- Suicide attempt or suicidal ideation within the last 12 months

*Other exclusion criteria:*

- Severe hypertension > 180/100 mmHg

